3.2.3 Physical Examination and Vital Signs

3.2.3.1 Physical examination

The following body systems should be evaluated as “normal” or “abnormal” by the Investigator, at the visits per the Schedule of Assessments:

- Skin
- Cardiovascular system
- Respiratory
- Abdomen
- Head and neck
- Musculoskeletal system
- Neurological function (mental status exam [level of consciousness, cognitive function], cranial nerve assessment, reflex testing, motor system assessment, sensory system assessment)
- Lymph nodes
- Psychological

Weight will be recorded every time a physical examination is performed and height will be evaluated at Screening Visit only.

The Investigator may choose to further investigate any other sign that he/she observes during the physical examination.

3.2.3.2 Vital signs

Systolic and diastolic blood pressures and pulse rate will be performed after 5 minutes rest in sitting position.

4 EFFICACY AND SAFETY VARIABLES

4.1 Efficacy Variables

- Percentage of subjects with an IGA Score of 0 (clear) or 1 (almost clear).
- Change from Baseline in Pruritus
- Change from Baseline in % BSA

4.2 Safety Variables

Key Safety variables are as follows:

- Key Laboratory Parameters:
 - Serum albumin-adjusted calcium
 - urine calcium : creatinine ratio,
 - phosphorus,
 - PTH.
- Adverse Events

5 POPULATIONS ANALYZED

5.1 Safety Population

The Safety Population is defined as all subjects who have applied the study drug at least once.

All statistical analyses will be performed based on the safety population.

Prior to the final database lock of the study, a data review will occur to assess the potential bias of any data issues for final statistical analyses. Subjects with major/minor protocol deviations will be identified in the data review meeting. No per protocol population will be defined.

6 SAMPLE SIZE CONSIDERATION

No formal sample size calculation has been performed. See Protocol Section 9.2 “Sample size determination”.

7 STATISTICAL METHODS AND DATA CONSIDERATIONS

SAS version 9.2 for windows will be used for all statistical analyses.

In general, the categorical variables will be summarized by frequency and percentage for each response category (N, %). The continuous variables will be summarized using means, medians, minimum, maximum, and standard deviations for the data collected at each visit.

7.1 Study Subjects

Subject disposition, demographics, baseline characteristics, previous and concomitant therapies, previous and concomitant procedures, and subjects with major protocol deviations will be summarized for the safety population.

7.1.1 Disposition of Subjects

The number of subjects and the number of subjects by site will be summarized in safety population.

The number and percentage of subjects who complete the study and subjects who discontinue from the study will be summarized as well as reasons for discontinuation. Discontinuation by site and by visit will be tabulated. The discontinued subjects will be listed with the reason for discontinuation, along with the relevant comments recorded on the CRF exit form.

7.1.2 Protocol Deviations

According to protocol deviation plan, protocol deviations will be tracked by Chiltern Insight System and reviewed periodically during regular study team meetings and prior to IDMC meeting (at least every 4 months). In the data review meeting prior to database lock, protocol deviations will be reviewed and be categorized to major / minor protocol deviations. The decisions of major or minor deviations will be based on the eligibility criteria, study conduct and/or the impact to the efficacy and safety results.

The major/minor protocol deviation will be detailed in evaluability criteria document prepared before data review meeting.

7.2 Efficacy Analysis

7.2.1 Data Sets Analyzed

All efficacy variables will be analyzed based on the Safety population.

7.2.2 Demographic and Baseline Characteristics

Demographic and Baseline characteristics will be summarized for the Safety population. Age will be summarized as a continuous variable. Gender, race, skin phototype, and age group (2-5 years, 6-12 years, 13-17 years) will be analyzed as categorical variables. Baseline IGA,

baseline pruritus, baseline percent body surface area involved and Maximum allowed Daily dose will be summarized as continuous variables.

Subjects rolling over from previous studies SPR.18132 and SPR.18102 will be tabulated (if needed) and listed with previous treatment and subject ID information.

7.2.3 Medical History, Previous and Concomitant Therapies/Procedures

Previous therapies are the therapies/medication with stop date at or prior to the first dose of study medication. Any therapy/medication usage post first dose of study medication are considered concomitant therapy.

Previous procedures are the procedures with stop date at or prior to the first dose of study medication. Any procedures post first dose of study medication are considered concomitant procedures.

Therapies/medication will be coded using WHODRUG dictionary (Version March 1, 2013). The number and percentage of subjects who take previous therapies and concomitant therapies will be summarized by ATC class and WHO DRUG in the Safety population, respectively.

Procedures will be coded using MedDRA dictionary (version 15.0). The number and percentage of subjects who take previous procedures and concomitant procedures will be summarized by System Organ Class and Preferred Term in the Safety population, respectively.

Medical history will be provided in a subject-by-subject listing.

7.2.4 Compliance

Compliance will be based on actual study drug exposure and expected study drug exposure. (Compliance = Actual study drug exposure /Expected study drug exposure). Compliance in days and compliance in doses are defined in Section 7.3.1.

7.2.5 Efficacy Analysis

No formal inferential statistical analysis will be performed. All efficacy data will be summarized as observed based on analysis visit as well as additional analysis visit of Week 26 (LOCF, last observation carried forward). (Section 7.5). Analysis visit of Week 26 (LOCF) will be assigned as the last available data (excluding unscheduled visit) during treatment period. If there is no data available post baseline, the baseline visit will be used.

IGA and pruritus will be summarized over time by each category and by shift change.

Observed and changes from baseline of the IGA, Pruritus, and Percent BSA over time will be summarized as continuous variables. Additionally, change from baseline in efficacy data over time will be presented graphically.

In addition, IGA, pruritus, and Percent BSA will be summarized descriptively by gender, race, and age group (2-5 years, 6-12 years, 13-17 years).

7.2.6 Statistical and Analytical Issues

7.2.6.1 Adjustment for Covariates

Not applicable as there is no formal inferential statistical analysis will be performed.

7.2.6.2 Handling of Dropouts or Missing Data

All data will be summarized as observed based on analysis visit as well as additional analysis visit of Week 26 (LOCF, last observation carried forward) (Section 7.6). If there is missing baseline data, screening visit data will be used.

Week 26 (LOCF) will be assigned based on last available data during the treatment period, including baseline.

7.2.6.3 Interim Analyses and Data Monitoring

No interim analysis is planned for this study.

7.2.6.4 Multicenter Studies

This is an open-label, uncontrolled, multicenter long-term safety and efficacy study. No center effect will be examined.

7.2.6.5 Multiple Comparison/Multiplicity

Not applicable.

7.2.6.6 Use of an Efficacy Subset of Patients

The Per-Protocol population (PP) is not planned for this study. Subjects who have protocol deviations will be identified during the data review meeting prior to database lock.

7.2.6.7 Active-Control Studies Intended to Show Equivalence

Not applicable.

7.2.6.8 *Examination of Subgroups*

Descriptive summaries of IGA, pruritus, and percent BSA will be performed by gender, race, and age group (2-5 years, 6-12 years, 13-17 years).

7.3 Safety Analysis

7.3.1 Extent of Exposure

7.3.1.1 Study Duration

Study duration is calculated as the date of the last visit including follow up period minus the date of the baseline visit plus one. Study duration will be summarized by descriptive statistics.

7.3.1.2 Treatment Duration

Treatment duration is calculated as the date of the last application minus the date of the first application plus one. If the date of the last application is not available, the date of the last visit during treatment period will be used in calculation. If the date of the first application is not available, the baseline date will be used in calculation.

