7.3.1.3 Study Drug Exposure

The study drug is applied twice daily. Temporary drug discontinuations and dose modifications is permitted in instances of out-of-range laboratory results, local tolerability issues, and clearing/worsening of disease. Subjects also have missed doses due to other unexpected reasons. Reason for missed doses (either temporary drug discontinuations or dose modification), incidence of temporary drug discontinuation and dose modification, and corresponding duration will be summarized and examined.

Actual study drug exposure and expected study drug exposure will be calculated in two definitions (in days and in doses). Missed doses due to complete clearing of psoriasis (IGA=0) will be excluded from the expected exposure. Any other missed dose due to non-safety or safety reason, even protocol allowed, will not be deducted from the expected study drug exposure.

Actual study drug exposure in days = Treatment duration (days) – number of days with no applications in both PM and AM (temporary drug discontinuations).

Actual study drug exposure in doses = Treatment duration *2 – number of missed doses.

Expected study drug exposure in days = Treatment duration (days) – number of days with no applications due to complete clearing of psoriasis (IGA=0) only.

Expected study drug exposure in doses = Treatment duration * 2 – number of missed doses due to complete clearing of psoriasis (IGA=0) only.

Compliance will be based on actual study drug exposure versus expected study drug exposure. Compliance will be a good index of data integrity rather than protocol deviations

Compliance (%) in days = Actual study drug exposure in days /expected study drug exposure in days.

Compliance (%) in doses = Actual study drug exposure in doses /expected study drug exposure in doses.

Actual study drug exposure, expected study drug exposure, and compliance in two definitions (in days or in doses) will be summarized.

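### SAP compliance formula: doses missed after a child's last application leave the denominator, although the SAP allows only doses missed for complete clearing to be deducted

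*SAP*

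**What the plan says.** SAP 7.3.1.2 defines the duration: "Treatment duration is calculated as the date of the last application minus the date of the first application plus one". A visit date replaces the end of that interval in one case only: "If the date of the last application is not available, the date of the last visit during treatment period will be used in calculation".

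SAP 7.3.1.3 builds both parts of the compliance ratio on this duration:

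- Numerator: "Actual study drug exposure in doses = Treatment duration *2 – number of missed doses".
- Denominator: "Expected study drug exposure in doses = Treatment duration * 2 – number of missed doses due to complete clearing of psoriasis (IGA=0) only".
- Ratio: "Compliance (%) in doses = Actual study drug exposure in doses /expected study drug exposure in doses".

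The measure in days has the same structure: "Expected study drug exposure in days = Treatment duration (days) – number of days with no applications due to complete clearing of psoriasis (IGA=0) only".

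The same section states the rule that the formulas are meant to carry out. Doses missed for clearing are removed from expected exposure, and then: "Any other missed dose due to non-safety or safety reason, even protocol allowed, will not be deducted from the expected study drug exposure".

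Nothing else in the SAP extends expected exposure to Week 26 or to the child's exit from treatment. Protocol 9.1.5 says only that exposure and compliance will be summarized.

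**The concern.** The rule and the formula treat the same doses differently. Under the rule, a dose missed for any reason other than clearing stays in the denominator. Under the formula, this is true only if the child applies the drug again later. Once there is no later application, the duration ends and every subsequent missed dose disappears from numerator and denominator together.

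The protocol lets a child be off drug while still attending. Sections 5.6 and 6.4 provide for temporary stops for abnormal albumin-adjusted calcium, low PTH, other out-of-range laboratory results and local tolerability, and for several of these give no fixed restart date. SAP 7.3.1.3 also expects doses to be missed for other, unforeseen reasons. If such a stop never ends, or the family simply gives up applying the ointment, the child's compliance is calculated over the period before the stop alone. What is at stake is the compliance summary listed in SAP 9.1.

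**Working it through.** The documents give no compliance figure to reproduce. As a check on the time scale, the Week 26 target day is 26 × 7 + 1 = 183, which agrees with SAP Table 2.

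**Inputs**

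- Planned treatment: 26 weeks = 182 dosing days = 364 doses (twice daily).
- Last application date: Day 28 in the main example. This is an assumption; a range follows.
- Reason for stopping: not clearing. No doses missed before the stop. Visits attended to Week 26.

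**1. SAP formula as written**

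- Treatment duration = 28 − 1 + 1 = 28 days.
- Actual = 2 × 28 − 0 = 56 doses. Expected = 2 × 28 − 0 = 56 doses.
- Compliance = 56/56 = 100%. In days, 28/28 = 100%.

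**2. Expected exposure over the planned 26 weeks**

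- Compliance = 56/364 = 15.4%. In days, 28/182 = 15.4%.

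**3. Other stop days, same conditions**

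| Last application | SAP | Over 182 days |
|---|---|---|
| Day 14 | 100% | 7.7% |
| Day 28 | 100% | 15.4% |
| Day 56 | 100% | 30.8% |
| Day 84 | 100% | 46.2% |
| Day 140 | 100% | 76.9% |

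**4. More use, lower score**

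Let the Day 28 child dose again on Day 182 only. Duration becomes 182 days, with 153 days missed (Days 29 to 181). Actual = 182 − 153 = 29 days, and SAP compliance = 29/182 = 15.9%. One extra day of treatment moves the score from 100% to 15.9%.

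**5. Same use, different score**

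Suppose the Day 28 child has no recorded last application date and the last treatment-period visit is on Day 183. The fallback makes the duration 183 days, so expected = 366 doses. Missed doses for Days 29 to 183 are 155 × 2 = 310, so actual = 366 − 310 = 56, and compliance = 56/366 = 15.3%. With the date recorded, it is 100%.

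**6. The counting window for missed doses is not stated**

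If misses are counted to Day 182 while the duration stays at 28 days, there are 154 × 2 = 308 missed doses. Actual = 56 − 308 = −252 doses, and compliance = −252/56 = −450%. That cannot be intended, so the formula works only if misses are counted up to the last application, which is the reading used in step 1.

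**7. Two limits on the effect**

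- Earlier misses still count. With 6 doses missed in the 28 days, the SAP gives 50/56 = 89.3%, against 50/364 = 13.7%.
- A child who clears at Day 28 and stays clear scores 100% either way: over 182 days, expected = 182 − 154 = 28 days and actual = 28 days.

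**8. Effect on the mean (illustration only)**

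Assume k of 100 children stop at Day 28 as above and the rest are at 95%:

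| k | SAP mean | Mean with expected exposure over 182 days |
|---|---|---|
| 5 | 95.25% | 91.0% |
| 10 | 95.5% | 87.0% |
| 20 | 96.0% | 79.1% |

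The SAP mean rises as more children stop.

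**The case against.** The best defence is that the SAP measures adherence while on treatment. On that view a missed dose is one missed between first and last application, the formulas deduct only clearing doses within that span, and rule and formula agree. Step 6 gives this some support, since counting later doses gives an absurd result. But the SAP does not state that window. Its rule covers any reason except clearing, and the on-treatment reading keeps the reversal in step 4. SAP 7.3.1.3 describes compliance as an index of data integrity; a score that falls from 100% to 15.9% when a child uses more drug does not serve that purpose well.

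Other parts of the defence stand, and they rule out stronger conclusions that a reader might draw:

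- *That exposure is overstated.* It is not. SAP 7.3.1.3 summarizes actual exposure and the reasons for missed doses in their own right, and SAP 9.3 lists study duration, treatment duration and medication exposure tables. The example child appears there correctly, with 28 days and 56 doses.
- *That compliance underpins a claim of 26 weeks of twice-daily use.* Neither document gives it that role. Treatment is planned for up to 26 weeks, there is no per-protocol population, and no inferential test uses compliance.
- *That the poorest adherers generally score best.* A child who misses doses throughout but applies until Week 26 is fully penalized, as is one who resumes after a safety stop. Children discontinued for a two-grade worsening, IGA 4 or confirmed urolithiasis go to the Week 26/ET visit under Protocol 5.6. If that visit is prompt, their score hardly changes.

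**Conclusion.** Wrong as written; minor severity. The SAP's compliance formula does not carry out its own rule on missed doses. The error affects children who stop for a reason other than clearing, never restart and keep attending. For such a child with no earlier misses, the SAP returns 100% where the figure over the planned 26 weeks is 7.7% for a last application on Day 14, 15.4% on Day 28 and 76.9% on Day 140.

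The stop days are assumptions, and the documents give no basis for estimating how many children will follow this pattern, so the effect on mean compliance is unknown; the means in step 8 are illustrations. The consequence is confined to a descriptive ratio whose components are reported separately.

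**What to change.** For compliance only, define one window from the first application to the end of the child's treatment period: the Week 26/ET visit, or the withdrawal date if there is no such visit. Then, over that window:

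- calculate actual and expected exposure, in days and in doses;
- count missed doses for all reasons, and separately those missed for IGA 0;
- deduct only the IGA 0 doses from expected exposure.

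Both the durations and the counts must move to the new window. Changing the denominator alone leaves the numerator on a different time base. State whether the day of the final visit counts as a dosing day; this matters little (28/182 = 15.4%, 28/183 = 15.3%). Keep treatment duration, first to last application, as a separate exposure summary.

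No new data are needed: the dosing calendar in Protocol 6.3.4 already records the date and time of each application. The cost is a short revision of SAP 7.3.1.3 and its programming, and a mean compliance that will look somewhat less favourable.

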7.3.1.3 Study Drug Exposure

The study drug is applied twice daily. Temporary drug discontinuations and dose modifications is permitted in instances of out-of-range laboratory results, local tolerability issues, and clearing/worsening of disease. Subjects also have missed doses due to other unexpected reasons. Reason for missed doses (either temporary drug discontinuations or dose modification), incidence of temporary drug discontinuation and dose modification, and corresponding duration will be summarized and examined.

Actual study drug exposure and expected study drug exposure will be calculated in two definitions (in days and in doses). Missed doses due to complete clearing of psoriasis (IGA=0) will be excluded from the expected exposure. Any other missed dose due to non-safety or safety reason, even protocol allowed, will not be deducted from the expected study drug exposure.

Actual study drug exposure in days = Treatment duration (days) – number of days with no applications in both PM and AM (temporary drug discontinuations).

Actual study drug exposure in doses = Treatment duration *2 – number of missed doses.

Expected study drug exposure in days = Treatment duration (days) – number of days with no applications due to complete clearing of psoriasis (IGA=0) only.

Expected study drug exposure in doses = Treatment duration * 2 – number of missed doses due to complete clearing of psoriasis (IGA=0) only.

Compliance will be based on actual study drug exposure versus expected study drug exposure. Compliance will be a good index of data integrity rather than protocol deviations

Compliance (%) in days = Actual study drug exposure in days /expected study drug exposure in days.

Compliance (%) in doses = Actual study drug exposure in doses /expected study drug exposure in doses.

Actual study drug exposure, expected study drug exposure, and compliance in two definitions (in days or in doses) will be summarized.

7.3.2 Adverse Events

Adverse events will be coded using the Medical Dictionary for Regulatory Activities (MedDRA) dictionary (version 15.0).

Treatment-emergent adverse events (TEAEs) is defined as an AE with an onset date on or after the first application of the study drug. TEAEs will be tabulated in frequency tables by System Organ Class and Preferred Term for whole study and by period (Day 1 to Day 90, Day 91 to End of Treatment, Follow-up period). Additional summary tables will be provided for TEAEs that are considered serious (SAEs), related to the study drug(s), severe, and possibly related to Calcium Metabolism from predefined SOCs/HLGT . TEAEs of special interested and TEAEs leading to discontinuation will also be summarized. For a given TEAE, a subject will be counted once even if he/she has experienced multiple episodes of that particular TEAE. Subgroup summaries of TEAEs will be provided based on gender, race, and age group (2-5 years, 6-12 years, 13-17 years) when appropriate.

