### **1.1 Medical background and short rationale for the clinical trial**

Safety and efficacy of calcitriol 3 mcg/g ointment in pediatric subjects under the age of 12 has not been previously studied. The current study of the long-term safety of calcitriol 3 mcg/g ointment applied twice daily for up to 26 weeks is specifically designed to enroll and evaluate pediatric subjects 2 to 16 years and 11 months (Version R03) of age with mild to moderate plaque psoriasis. In addition, this study will allow the evaluation of plasma concentrations of calcitriol in a subset of 9 subjects aged 2 to 6 and 11 months.

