##### 9.1.1.2 *Key Safety Endpoints*

- Laboratory: Serum albumin-adjusted calcium, urine calcium : creatinine ratio, phosphorus, and PTH.
- Adverse Events

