### 9.1.5 Safety analysis methods

No inferential statistical analysis is planned for safety endpoints of the study.

The laboratory parameters at scheduled visits and change from Screening at post-baseline visit(s) will be summarized descriptively by treatment and by visit. A shift table for lab parameters at Screening versus Week 26/ET will be provided when appropriate.

Only Treatment-emergent Adverse Events (TEAEs) will be summarized. A TEAE is defined as an AE with an onset date on or after the first application of the study drug.

TEAEs will be tabulated in frequency tables by System Organ Class and Preferred Term based on the Medical Dictionary for Regulatory Activities (MedDRA). Additional summary tables will be provided for TEAEs that are considered serious (SAEs), related to the study drug(s), and severe. TEAEs that are AESIs, as well as TEAEs leading to discontinuation will also be summarized. For a given TEAE, a subject will be counted once even if he/she has experienced multiple episodes of that particular TEAE. Subgroup summaries of TEAEs will be provided based on gender, age group, and race when appropriate.

Prior and concomitant therapies and procedures will be summarized. A prior therapy/procedure is one that ends at or before baseline; and a concomitant therapy/procedure is one starting after the baseline visit.

Extent of study drug exposure and compliance will also be summarized.

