### **9.1.8 Subgroup analyses**

Subgroup analyses for safety data will be performed by age group, gender, and race. Details will be provided in the SAP.

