7.3.3 Laboratory Parameters

Analysis visit will be applied for the laboratory parameter summaries.

Descriptive statistics for each laboratory parameter will be provided for scheduled visit and for the changes from Screening at each post-baseline visit. “Final” visit (Week 26 (Final)) will be defined as the last post-baseline available observation during the treatment period.

A shift table for the laboratory data at Screening versus Final will be constructed for laboratory parameters for which numeric reference ranges are available. The number of subjects below, within, and above the laboratory reference ranges at Screening versus Final will be summarized.

For each laboratory test, a complete data listing will be provided for subjects who have any laboratory results outside the reference ranges, and for subjects who have any laboratory results with clinical significance.

Plot of mean change from screening and spaghetti plot (all-subjects-in-one figure or selective individual subject figure) will be used to explore the trend of laboratory data change over the study, especially for serum albumin-adjusted calcium, urine calcium/creatinine ratio, phosphorus, PTH. Box-and-Whisker plots for PTH and Calcium/Creatinine ratio by visit will be constructed for data exploration.

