8 CHANGES FROM THE PROTOCOL ANALYSIS PLAN

No change from protocol analysis plan.

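### The SAP plans no age-group summary of the key laboratory safety endpoints, although protocol 9.1.8 plans safety subgroups by age, and its age bands cannot isolate children under 12

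*SAP*

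**What the plan says.** Protocol 9.1.8 states: "Subgroup analyses for safety data will be performed by age group, gender, and race", and leaves the details to the SAP. Protocol 9.1.1.2 names the key safety endpoints as adverse events and "Laboratory: Serum albumin-adjusted calcium, urine calcium : creatinine ratio, phosphorus, and PTH". Protocol 9.1.5 is narrower: "Subgroup summaries of TEAEs will be provided based on gender, age group, and race when appropriate". The synopsis likewise mentions subgroups for adverse events only.

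In the SAP, 7.3.2 gives subgroup summaries of TEAEs by gender, race and "age group (2-5 years, 6-12 years, 13-17 years) when appropriate". Sections 7.2.5 and 7.2.6.8 use the same three bands for IGA, pruritus and percent BSA, and 7.2.2 uses them for baseline. For laboratory data, 7.3.3 says: "Descriptive statistics for each laboratory parameter will be provided for scheduled visit and for the changes from Screening at each post-baseline visit". It adds a Screening-versus-Final shift table, listings and plots, with no subgroup. SAP section 8 reads: "No change from protocol analysis plan".

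On why age matters, protocol 1.1 says: "Safety and efficacy of calcitriol 3 mcg/g ointment in pediatric subjects under the age of 12 has not been previously studied". Protocol 5.3 sets the current age range at 2 years to 16 years 11 months.

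**The concern.** The trial's main safety question is calcium homeostasis in children, and it is answered mostly by laboratory values. The SAP provides age subgroups for efficacy, which protocol 9.1.8 does not ask for. It omits them for the laboratory endpoints, which a plain reading of 9.1.8 covers. If calcium or PTH moved in younger children only, the planned laboratory tables would show that movement averaged with the older children, and no planned table would separate the two. Even the age tables that do exist cannot be read as under 12 against 12 and over, because the middle band straddles that age. If the laboratory tables and bands are chosen after the data are seen, they will carry less weight than if they are fixed now.

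**Working it through.** **1. The plan's own figure.** No figure in the plan bears on age subgroups. The only sample-size figure reproduces: 100 / (1 − 0.40) = 166.7, rounded up to 167 screened. No age distribution or age quota is given, apart from a PK subset of about 9 children aged 2 to 6 years 11 months.

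**2. Which outputs are split by age.**

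| Data | SAP text | SAP table list | Split by age? |
|---|---|---|---|
| IGA, pruritus, % BSA | 7.2.5, 7.2.6.8 | 9.2 | Yes |
| TEAEs | 7.3.2 | 9.3 (two tables) | Yes |
| Albumin-adjusted calcium, Ca:Cr, phosphorus, PTH | 7.3.3 | 9.3 (summary, shift table, listings) | No |

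Protocol 9.1.1.2 lists five key safety items: four laboratory parameters and adverse events. One of the five has an age summary.

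**3. Whether the TEAE tables could stand in.** Under protocol 7.2.2, a post-screening laboratory value becomes an adverse event only if three things hold. It is out of range, it suggests disease or organ toxicity or is judged pathological, and it is new or worse since screening. A consistent shift within the reference range meets none of the TEAE-by-age tables.

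**4. Mapping the bands.** By completed years of age, the protocol range covers 15 single years (2 to 16).

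| SAP band | Single years within 2–16 | Under 12 | 12 and over | Share if ages were uniform |
|---|---|---|---|---|
| 2–5 | 4 | 4 | 0 | 4/15 = 27% |
| 6–12 | 7 | 6 | 1 | 7/15 = 47% |
| 13–17 | 4 | 0 | 4 | 4/15 = 27% |

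The under-12s are 4 + 6 = 10 single years, and no band or sum of bands equals them; the two lower bands together hold 11. With uniform ages (an assumption), 12-year-olds are 1/7 = 14% of band 6–12. If they were half or twice as frequent as each other year, the share would be 0.5/6.5 = 8% or 2/8 = 25%. The PK age range is also cut: ages 2 to 5 fall in the first band and 6-year-olds in the second. The top band's label runs one year past the current upper age limit.

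**5. Cell sizes with edges at 7 and 12.** Ages 2–6, 7–11 and 12–16 are five single years each, so uniform ages give 5/15, about 33 of 100 subjects per band. The youngest band could be much smaller; the only figure the documents give for those ages is the PK subset of about 9. If no subject in a band of size n has an out-of-range value, the exact one-sided 95% upper limit on the true rate is 1 − 0.05^(1/n). That is 28.3% for n = 9, 8.7% for n = 33 and 3.0% for n = 100.

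**The case against.** The strongest reply is that the SAP follows the protocol's operative text. Section 9.1.5 and the synopsis limit subgroups to adverse events where appropriate, 9.1.5 describes the laboratory summaries with no subgroup, and 9.1.8 hands the details to the SAP. This has force: the protocol is uneven, and a reader who infers plain breach of an unambiguous promise goes too far. But the narrower sentences do not cancel the broader one, and leaving details to the SAP is not leave to drop the laboratory endpoints without saying so. The inconsistency needs a recorded decision, and section 8 of the SAP records none.

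A second reply is that individual signals are already caught. Pathological laboratory changes become adverse events and so reach the by-age TEAE tables. Out-of-range listings and individual plots are planned, and under protocol 7.2.2.1 the IDMC is alerted to hypercalcemia and to 30% falls in PTH. All of this stands as subject-level protection. None of it summarises change in the four parameters by age.

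Third, the SAP calls its table list tentative and still describes 140 subjects and visits at Weeks 8 and 20, so it needs revision anyway. That makes the change easier; it does not make it unnecessary.

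Fourth, the PK objective does not depend on the bands. Protocol 9.1.6 analyses PK by paired comparisons and correlation within the PK subset, which also requires at least 3% BSA. A 2 to 6 years 11 months band would match the PK age range but would not reproduce that subset. This objection stands, so an edge at 7 years is optional.

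**Conclusion.** The point holds and should be settled before database lock. Four of the five listed key safety endpoints have no age summary, against the broader wording of protocol 9.1.8, and the SAP's bands cannot isolate the under-12s. This rests on reading safety data in 9.1.8 as including the key laboratory endpoints, which 9.1.1.2 supports. No data collection, visit or conduct of the trial is affected.

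A reader might infer more than the documents support:

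- **That the trial exists to study the under-12s or the PK subset.** The primary objective in protocol 2.1 covers the whole age range. Under 12 is the evidence gap named in the rationale, and PK is a secondary objective in about 9 children.
- **That 12-year-olds are already studied.** The adolescent study in protocol section 1 had 25 subjects, a mean age of 14.7 years and 21 days of treatment. It does not supply 26-week safety at age 12.
- **That younger children necessarily have a higher permitted dose per kilogram.** Appendix 4 sets the ceiling by weight, and it is the same 0.5 g/kg for everyone up to 28 / 0.5 = 56 kg, adolescents included.
- **That the dilution can be sized.** If an effect occurred only in a share p of subjects, the pooled mean change would show p times that effect. With p unknown, any percentage only restates the assumption, and it would not apply to shift counts or listings.

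The top band's overrun is minor. Protocol 10.5.2 keeps subjects already enrolled on the earlier protocol, and the SAP gives that age range as 2 to 17, so some 17-year-olds may be in the data.

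**What to change.** 1. In SAP 7.3.3 and 9.3, add descriptive summaries by age group for albumin-adjusted calcium, urine calcium:creatinine ratio, phosphorus and PTH: change from Screening by visit, out-of-range counts, and the Screening-versus-Final shift table.
2. Use one set of age bands with an edge at 12 years throughout the SAP (7.2.2, 7.2.5, 7.2.6.8, 7.3.2 and 7.3.3), so that baseline, efficacy, TEAE and laboratory tables share a single scheme. Bands of 2 to 6 years 11 months, 7 to 11 years 11 months, and 12 to 16 years 11 months would also match the PK age range; the edge at 7 is optional. State where any 17-year-old enrolled under the earlier protocol is counted.
3. Reconcile protocol 9.1.5 and the synopsis with 9.1.8. If laboratory subgroups are to be left out, say so with the reason in SAP section 8.

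The cost is a few more descriptive tables from data already collected, with no new visits, samples or inference. The downside is small cells in the youngest band. Counts should be shown beside percentages, and an absence of abnormal values there should not be read as evidence that the rate is low.
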